Estimating Site Performance 2 (ESP2) Study Protocol

Version: v1.0

16/8/2019

Lead investigator

[name]

Co-investigators

[name], [name]¹, [name]¹, [name], [name], [name]², [name]¹, [name]¹, [name]

1. Health Services Research Unit, University of Aberdeen, Aberdeen
2. UK Trial Managers' Network, University of Nottingham, Nottingham
3. NRS Cancer Research Network, Aberdeen Royal Infirmary, Aberdeen

Funding

Web-development funded by the University of Aberdeen Development Trust. Website maintenance funded from the Health Research Board (Ireland) grant HRB-TMRN-2017-2.

Hosted by

CHaRT, [name], University of Aberdeen

STUDY SUMMARY

Question asked – Can a guided trial prediction form for trial managers be used as a way of predicting which trial sites will recruit to target?

Considered for entry – Trial managers anywhere in the world who are working on randomised or non-randomised trials of interventions.

Populations – Trial managers (or other individuals) responsible for recruitment site set-up and carrying out site initiation training.

Outcome assessment – a) Can trial managers predict if local recruitment sites will recruit to the predicted target b) what are the most important factors (from eight alternatives) of the prediction.

INTRODUCTION

Background

A large investment of public money is made by the UK each year to fund large multicentre clinical trials. ‘Treatment evaluation’, largely trials, represents 8.5% of total spending by the 12 main public and charitable funders of health research in the UK, or £140 million (UK Clinical Research Collaboration 2012). ‘Treatment evaluation’ represents over a third of NIHR funding and nearly half of MRC funding. The UK pharmaceutical industry spends nearly £5 billion on research and development every year (Department for Business 2011). Reviews have found that many (around half) of these studies will not recruit to target and need extensions, revisions to the sample size (power of the study) or need to be closed, which essentially leaves the clinical question unanswered (McDonald et al 2006; Bower et al 2007; Sully et al 2013). The NIHR would ideally like to see a greater participation in health research from patients and health care professionals (Department of Health 2006). However, money to increase the amount of research will be directed away from additional research if trials fail or have to be extended to achieve the required outcome targets. Trials have had to become more pragmatic to fit in with patients and health care professionals (Campbell et al 2007). Business models for running clinical trials have been shown to be good strategies for running more effective trials (Francis et al 2007; McDonald et al 2011). However, hold ups in obtaining local hospital R&D approval are still being observed (Kearney et al 2014; Treweek et al 2013) as are the efficient recruitment of participants (Bower et al 2014). These are just some of the many reasons that contribute to the high failure rates of trials.

One potential reason for failure that has had little consideration is that some local sites just fail to perform as recruitment centres and never fulfil their predicted potential. This was explored by our pilot work– the ESP study (Bruhn et al 2019). Ten trial managers working across eight trials made predictions for 56 site visits. Trial managers’ sensitivity was 82% and their specificity was 32%, correctly identifying 65% of sites that would hit their recruitment target and 54% of those that did not. Eight ‘red flags’ for recruitment failure were identified: previous poor site performance; slow approvals process; strong staff/patient preferences; the site recruitment target; the trial protocol and its implementation at the site; lack of staff engagement; lack of research experience among site staff; busy site staff. We used these red flags to develop a guided prediction form.

ESP2 will test the guided prediction form in a much larger study involving trial managers from across the UK and the world. ESP2 is a collaboration with the UK Trial Managers’ Network (<https://www.tmn.ac.uk/>) of over 1200 trial managers.

Rationale for study

A great amount of time, effort and cost is taken in setting up local recruitment sites for clinical trials. Many of the local sites will have been identified by a trial’s chief investigator because of eminent individuals working in the clinical area at the site, or through personal acquaintances. Alternatively,

local sites may have been put forward by the hospital's Research & Development departments, sometimes without prior contact with the local consultant who is expected to act as principal investigator. Another route for attracting local sites is promoting the trial and then interested clinical staff approach the trial office. Regardless of how a site is identified as a potential recruiter, it would be ideal to have a way to potentially predict whether the site would be a "good" site to have involved in the trial (in this context, to determine "good", we are focusing on recruitment).

In other words, is there a good way of making decisions about which sites are worth investing energy in, and which are not? ESP2 focuses on looking at this issue at the site set-up stage, once the site initiation training has been done.

OBJECTIVES

Is there a good way of making decisions about which local recruitment sites are worth investing energy in when setting up a clinical trial?

ESP2 hypothesises that trial managers who use the guided prediction form will be able to predict whether a site will be a 'good' site and recruit to target. If confirmed, such knowledge would enable energy and resources to be targeted more effectively using a simple form together with trial managers' experience.

OUTCOME MEASURES

Primary outcome measure

- The primary outcome is the proportion of correct predictions made by trial managers of sites that fail to recruit .

Secondary outcomes

- The impact each of the eight red flags has on recruitment predictions.

RESEARCH METHODS

The dedicated trial managers who handle local site set-up are deeply involved in this process and will (we speculate) have a good sense of whether a site will go on to recruit to its target. ESP2 asks trial managers to use our guided prediction form to predict site recruitment, which we will then compare to actual recruitment performance. If the form helps prediction, it could be rolled out as a trial management tool to enable time and energy to be directed to sites with a good chance of recruitment success, and prevent it being wasted on sites that are highly unlikely to meet their targets. It could also be a useful tool to help less experienced trial managers.

STUDY DESIGN

Inclusion criteria

- The people providing predictions must be trial managers responsible for setting up trial recruitment sites and carrying out site initiation training with site staff. Some people undertaking this activity may have a different job title; they will be eligible to take part on the basis of undertaking this activity.
- The recruitment prediction is for a site in a randomised or non-randomised trial. The site and the individual making the prediction can be anywhere in the world.
- The trial must be testing one or more interventions.
- The trial must be opening new recruitment sites.
- Individuals should be willing to make at least one prediction. These predictions can be for different sites within the same trial, sites across many trials, or a combination of both. There is no limit to the number of predictions a trial manager can make.

Exclusion criterion

- Cluster randomised trials.

Proposed start date and end date

Start: Autumn 2019.

End: Once we have around 1000 predictions. We expect that this may take up to two years, plus a further six months to allow the sites involved in the last predictions to do some recruitment.

Recruitment

Trial managers will be recruited by a variety of approaches: through UK Trial Managers' Network (e.g. we will ask trial managers to take part via email correspondence, and via flyer/presentation at the UKTMN Annual Meeting. We will also run a UKTMN webinar to raise awareness and support recruitment), within the Aberdeen Trials Unit, by word of mouth at meetings with staff at other Trials Units, through the five Trial Forge Centres (Aberdeen, Bristol and Cardiff in the UK; Basel in Switzerland; Brisbane in Australia) and by twitter. We will also use study flyers to promote the study, based on the template in Appendix 1 and incorporating study updates as the study progresses. All of these approaches will be used regularly until we reach 1000 trial manager recruitment predictions (see '*Sample size*').

Information about ESP2 will be provided on a dedicated website

(<https://w3.abdn.ac.uk/hsru/ESP2/Public/Public/index.cshtml>), managed by the Centre for

Healthcare Randomised Trials, CHaRT) for trial managers who consider taking part. Trial managers who do want to take part need to register their interest through the website and this registration will be taken as their consent to take part. Each trial manager will be given a unique identifier and will remain anonymous in all our reporting.

WHEN SHOULD TRIAL MANAGERS MAKE THEIR PREDICTIONS?

Trial managers should make predictions soon after completing the site initiation training. The site does not need to be open for recruitment when the prediction is made, so long as the site initiation training has been done.

DATA COLLECTION

Brief demographic information about the trial manager will be collected through the study website at registration. In addition, brief details about the trials the trial manager wishes to make predictions for will also be collected through the study website.

Trial managers will then be asked to fill in a short, online questionnaire for each site they carry out site initiation training for, and give a prediction as to whether that site is likely to meet its recruitment target. Trial managers will also be asked to pick the three red flags on our prediction questionnaire that were most important for their prediction. Trial managers may not wish to make predictions for all sites; they are not required to do so. However, there is no limit to the number of predictions a trial manager can make (although they should not make multiple predictions for the same recruitment site for the same trial).

Follow-up

Trial managers will be asked to tell us the total recruitment at each site for which they made a prediction 6 months after their prediction and again at 12 months after the prediction. This request will be sent automatically to trial managers via the study website.

This will give us actual site recruitment, which we can then compare to the target recruitment that the trial manager gave when making his or her prediction. For example, a trial manager may say that the recruitment target for a site is 80 participants at 12-months. She predicts recruitment failure at this site. At 6 months the trial manager tells us actual recruitment is 34 and at 12-months actual recruitment is 67. Her prediction of recruitment failure was correct.

At each timepoint we will also include an update option in case the site has been closed or the recruitment timeline amended.

Withdrawal

Trial managers are free to withdraw from taking part in ESP2 at any point during the study. Trial managers are encouraged to complete a prediction form for every site they complete site initiation training for but are able to participate to whatever extent they wish – for example, they may complete prediction forms for some but not all sites that they carry out site initiation training for.

If a trial manager withdraws because he or she is moving to a new post, we will encourage the replacement trial manager to register if he or she wishes to, in order to provide predictions and/or recruitment updates. This will help to reduce missing data.

Sample size

Our sample size decisions have been guided by [name], statistician and Director of CHaRT.

We are interested in the ability of trial managers to correctly identify a site that will fail to recruit. For a diagnostic test this is called specificity, the proportion of correct negatives. Our pilot work found a specificity of 32% (Bruhn et al 2019). We expect the eight red flags to improve this substantially because they were identified through qualitative work in our pilot as markers of poor recruitment.

The sample size is dependent on assumptions about prevalence (the proportion of sites that fail to recruit), sensitivity and specificity. The specificity of 32% seen in the pilot *without* the use of the red flags is too low for trial management decision-making. Instead we believe a 75% specificity is what we should target– it is high enough that the prediction cannot be ignored – and we want to be certain that the 95% confidence interval around a result of 75% has a lower bound above 65% (i.e. we want some certainty that our specificity is not actually much lower than 75%).

Our pilot (Bruhn et al 2019) had a recruitment failure prevalence of 40% of sites. The sensitivity in the pilot was 82%.

Therefore, if we take a recruitment failure rate of 40%, a sensitivity of 90% (a bit higher than the pilot because we expect the red flags to help here too) and the measured specificity of 75% that we want, a sample size of 1000 predictions would give us 80% power to rule out specificity of below 70%. Halving the sample size to 500 and with 40% prevalence, 90% sensitivity and a measured specificity of 73%, we'll still have adequate power to rule out a lower bound to of 65%.

Therefore, we will aim for 1000 predictions. However we would still have acceptable power, based on reasonable assumptions, providing we reach 500 predictions. In our pilot we got 56 predictions from one trials unit, ten trial managers and eight trials. In the UK as a whole there are 51 registered trials units and well over 1200 trial managers. Each trials unit is likely to have a portfolio of at least ten trials. Clearly, our web-based study is open to trial managers well beyond the UK. The pool of potential predictions is therefore very large. A target of 1000 predictions is not at all implausible.

ANALYSIS

Demographic information for trial managers and trials will be reported in frequencies and percentages. Site recruitment will be recalculated to be *pro rata* to the duration given for the target (i.e. if recruitment runs for two years but we measure at one year, we will halve the recruitment target we judge the prediction against). This does make the assumption that recruitment is constant across the period but we think one year should be long enough for recruitment to have settled to its steady-state. Sites will be deemed to have met their recruitment target if they hit or exceeded that target. We will calculate specificity and sensitivity as well as positive and negative predictive values.

If data allow, we will do three pre-planned subgroup analyses:

1. Explore the effect of trial manager experience on prediction accuracy.
2. Explore whether prediction accuracy for randomised trials differs from that for non-randomised trials.
3. Explore whether prediction accuracy varies by disease area.

Our earlier study (Bruhn et al 2019) found some suggestion of a link between experience and prediction accuracy and whether a trial was randomised or not and prediction accuracy. As ESP2 is much bigger, we may be able to draw more certain conclusions as to whether relationships do exist.

RESEARCH GOVERNANCE

The University of Aberdeen Research Governance Manager has confirmed that this study does not require NHS REC or NHS R&D management approval. The University of Aberdeen Research Governance Manager has indicated that formal Sponsorship of the study is not required. The study will be submitted to the University of Aberdeen College of Life Sciences and Medicine Ethics Review Board (CERB) review. The study is very low risk.

FINANCE

Web-development was funded by the University of Aberdeen Development Trust. Website maintenance was funded from the Health Research Board (Ireland) grant HRB-TMRN-2017-2. ESP2 incurs only minor costs in terms of trial manager time but this will be borne by the institutions for which the trial managers work. Funding for dissemination will either be sought from internal department funds or from external sources as necessary.

DATA HANDLING

The website has been developed by data management staff at CHaRT and complies with GDPR. Staff taking part in the study will be assured that all predictions will be kept confidential. It will not be possible to identify individual recruitment sites or trials in reports from the study. Data will be kept for 3 years after publication and will be available from the project team on reasonable request and taking care to avoid identifying trials and trial managers.

STUDY MANAGEMENT

The study will be managed by the investigators listed above. Participating trial managers will be able to contact any of the investigators for information about the study, or if they have queries via an ESP2 mailbox.

END OF THE STUDY

The study will run until we have 1000 predictions, which we expect to take no more than two years. If at two years, we have more than 500 predictions but fewer than 1000, we will stop the study for new predictions. An additional six months beyond this point will allow some recruitment at sites involved in predictions made at the end of the prediction period. Analysis will occur after this time.

AUTHORSHIP AND PUBLICATION

We will follow International Committee of Medical Journal Editors (ICMJE) guidelines on authorship (see <http://www.icmje.org/recommendations/browse/roles-and-responsibilities/defining-the-role-of-authors-and-contributors.html>).

This work will be disseminated at meetings and conferences such as the UK Trial Managers' Network Annual Meeting, Society of Clinical Trials Conference and the International Clinical Trials Methodology Conference. The results will also be published in a peer reviewed journal. In any publication resulting from this work, it will not be possible to identify individual trial managers, trials or sites. Trial managers who contribute predictions and recruitment data to the ESP2 study will be appropriately acknowledged. A summary of results will be sent to all participating trial managers by email.

REFERENCES

Peter Bower, Valerie Brueton, Carrol Gamble, Shaun Treweek, Catrin Tudur Smith, Bridget Young, Paula Williamson (2014) Interventions to improve recruitment and retention in clinical trials: a survey and workshop to assess current practice and future priorities. *Trials* 15:399.

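### The primary outcome and its 75% benchmark rest on specificity alone, which rises whenever managers predict failure more often, so meeting the benchmark does not show that they can tell good sites from poor ones

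*Protocol*

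**What the plan says.** Protocol, Outcome Measures: "The primary outcome is the proportion of correct predictions made by trial managers of sites that fail to recruit". The only secondary outcome listed there is the impact of the red flags.

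Protocol, Sample size, names the measure: "For a diagnostic test this is called specificity, the proportion of correct negatives". It then sets the standard: "Instead we believe a 75% specificity is what we should target", because "it is high enough that the prediction cannot be ignored". Two lower bounds follow. One is a precision aim: "we want to be certain that the 95% confidence interval around a result of 75% has a lower bound above 65" per cent. The other is a power statement: "a sample size of 1000 predictions would give us 80% power to rule out specificity of below 70" per cent. A sensitivity of 90% enters only as a planning assumption.

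Protocol, Background, gives the only comparator: "Trial managers’ sensitivity was 82% and their specificity was 32" per cent, from 56 pilot predictions. There is no concurrent group without the form.

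Protocol, Analysis, plans sensitivity and both predictive values as well as specificity, but attaches no target to them. Research Methods gives the intended use if the form helps: to "enable time and energy to be directed to sites with a good chance of recruitment success".

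**The concern.** The hypothesis in Objectives is that managers using the form can predict whether a site will be a good one. That is a claim about discrimination. Specificity looks only at failing sites. It takes no account of recruiting sites wrongly predicted to fail, and a manager who predicted failure everywhere would score 100%.

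The form puts eight reasons for failure in front of the manager, so it could make managers readier to predict failure without making them better at it. The benchmark would record that as success. What matters to a trial acting on a predicted failure is the chance that the site really fails. In the Protocol's orientation (recruiting to target is the positive result) that is the negative predictive value (NPV). Specificity alone does not determine it.

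**Working it through.** **Inputs.** Failure prevalence 40%, planned sensitivity 90%, planned specificity 75%, N = 1000, bounds 65% and 70% (Sample size); pilot sensitivity 82% and specificity 32% (Background). At N = 1000 there are 400 failing and 600 recruiting sites. Predictions are treated as independent throughout.

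**The plan's own figures.**
- *Pilot.* The percentages are reproduced by 28/34 recruiting sites and 7/22 failing sites called correctly. These counts are reconstructed, not stated. They give a positive predictive value of 28/43 = 65% and an NPV of 7/13 = 54%.
- *Power.* The stated 80% against a 70% bound does not reproduce. With 400 failing sites and true specificity 75%, power at two-sided 5% is 57% (exact binomial), 59% (null-variance normal) or 64% (Wald). This is a separate matter; the point below does not depend on it.

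**1. Guessing, with no model.** Suppose failure is predicted for a random fraction q of sites. Then specificity = q, sensitivity = 1 − q, and the Youden index J = sensitivity + specificity − 1 = 0. At q = 0.75:
- NPV = 0.4×0.75 / (0.4×0.75 + 0.6×0.75) = 0.30/0.75 = 40%, the base rate.
- The probability that the lower 95% limit clears 65% with 400 failing sites is 99% (exact binomial, 280 or more correct calls needed).

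The stricter bound does not help. At q = 0.80 the 70% bound is cleared with probability 99.7% (normal approximation), and NPV is still 40%.

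**2. Threshold shift with pilot discrimination unchanged.** This uses an equal-variance normal model, which is an assumption.
- d′ = z(0.82) + z(0.32) = 0.915 − 0.468 = 0.448.
- Sensitivity at 75% specificity = Φ(0.448 − 0.674) = 41%. Holding J constant instead gives 39%; holding the diagnostic odds ratio constant gives 42%.
- NPV = 0.30 / (0.30 + 0.6×0.59) = 0.30/0.654 = 46%.
- Accuracy = 0.6×0.41 + 0.4×0.75 = 55%, against 0.6×0.82 + 0.4×0.32 = 62% at the pilot threshold.

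**3. The planned case, 90%/75%.** NPV = 0.30 / (0.30 + 0.6×0.10) = 0.30/0.36 = 83%.

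The same primary result of 75% therefore goes with an NPV of 40%, 46% or 83%.

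**4. Does a joint measure separate these cases?** SE(J) = √[sens(1−sens)/600 + spec(1−spec)/400].

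| Case | Sens / spec | J | 95% CI |
|---|---|---|---|
| Planned | 90% / 75% | 0.65 | 0.60 to 0.70 |
| Pilot sensitivity kept | 82% / 75% | 0.57 | 0.52 to 0.62 |
| Threshold shift only | 41% / 75% | 0.16 | 0.10 to 0.22 |
| Guessing | 25% / 75% | 0.00 | −0.05 to 0.05 |

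The pilot's J is 0.82 + 0.32 − 1 = 0.14. The first two cases clear it easily. The threshold shift clears it with probability about 10% (it is not zero because under this model J rises slightly, to 0.16). Guessing essentially never does.

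**5. Precision of the pilot.** SE = √(0.824×0.176/34 + 0.318×0.682/22) = 0.119, so the approximate 95% CI for J is −0.09 to 0.37. The figures in step 2 are illustrative; step 1 does not use the pilot.

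**The case against.** The strongest reply is that nothing is lost. Analysis already plans sensitivity and both predictive values, and NPV is the very quantity a trial would act on. A reader might infer from the choice of primary outcome that a threshold shift could not be told apart from better discrimination. The documents do not support that: the planned output would show the difference, as the separated intervals in step 4 confirm. This stands. The weakness lies in the declared outcome and benchmark, not in the data.

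A reader might also infer that prompting with eight red flags will probably push managers towards predicting failure. The Protocol does not show this. The form is not reproduced, and Sample size expects sensitivity to rise as well. A shift is possible; its likelihood is unknown.

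Third, the Protocol has no formal adoption rule, and the 75% stands in the sample-size section. It would go too far to say that effort will be withdrawn from good sites on specificity alone. But the 75% is the only level of performance the Protocol declares adequate. If specificity and NPV disagreed, whether the form had succeeded would be settled after seeing the results.

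A natural remedy, requiring the lower 95% limit of sensitivity to reach the pilot's 82%, is poorly chosen. A form that kept sensitivity at 82% and raised specificity to 75% would lift NPV from 54% to 0.30/(0.30 + 0.6×0.18) = 74% and accuracy from 62% to 79%. It would still fail that rule about 98% of the time.

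**Conclusion.** The point holds in this form: as the primary outcome and the only benchmark, specificity cannot by itself test the hypothesis in Objectives. Uninformative guessing at a 75% failure-call rate would meet the 65% bound about 99% of the time at 400 failing sites. That result needs only the Protocol's prevalence and independent predictions. The contrast between an NPV of about 46% and 83% also rests on the assumed normal model and on an imprecise pilot, and should be read as an illustration. The planned secondary measures would reveal a threshold shift, so this is a flaw in what the study declares as success, not an inability to see what happened.

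Clustering by manager and trial is ignored, and managers may make any number of predictions, so real intervals would be wider. Even with the standard error doubled, the lower limit of J in the planned case is about 0.65 − 1.96×0.050 = 0.55.

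**What to change.** In Outcome Measures and Sample size, make the benchmark joint. Both conditions must be met:

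1. The lower 95% limit of specificity exceeds one stated bound. Sample size gives both 65% and 70%; choose one.
2. The lower 95% limit of sensitivity + specificity − 1 exceeds the pilot's 0.14.

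Report NPV (the proportion of predicted-fail sites that fail) with its confidence interval as a key result, beside the observed failure rate. The second condition is a modest bar taken from an imprecise pilot: it screens out guessing and usually a pure threshold shift, while NPV shows how useful a predicted failure is.

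The cost is wording. No further predictions or data items are needed, since the counts are already collected. The downside is one more condition to meet, which at 1000 independent predictions is met easily at 90%/75% and at 82%/75%.

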Setting up trial sites takes up time, effort and cost. Not all of this is worth it because not all of those sites will recruit as planned. This is a shame because those sites that do not recruit as planned are likely to take up just as much, or perhaps more, trial manager time as sites that do recruit. What would help would be some way to predict whether a site would be a “good” site to have involved in the trial as far as recruitment is concerned. In other words, is there a good way of making decisions about which sites are worth investing energy in, and which are not?

The Estimating Site Performance–2 project (ESP2) project aims to test a tool that just might help. The project is led by trial managers based at the University of Aberdeen, UK and asks trial managers to make predictions about site recruitment after carefully considering eight ‘red flags’ for poor recruitment. These flags (e.g. lack of site staff engagement, or previous poor performance) were developed in the original ESP project, which was published in 2019 in *Trials* (<https://trialsjournal.biomedcentral.com/articles/10.1186/s13063-019-3287-6>).

The UK Trial Managers’ Network (UKTMN; <http://www.tmn.ac.uk>) has partnered with Trial Forge (<https://www.trialforge.org>) to support ESP2. The project needs 1000 recruitment predictions from trial managers so it is likely that trial managers across the world can play a role. Predictions will be made online and the web-based system is due to be launched in early autumn 2019. After a prediction has been

made, the ESP2 team will contact you six months later and then again at 12 months to see how recruitment is going.

We all know that sites that don't recruit are a problem. ESP2 aims for a tool that supports trial managers' hunches about site recruitment that is backed up by a 1000 predictions, from hundreds of trial managers, in dozens of trials and which makes those hunches too compelling for anyone to ignore.

You can find out more about ESP2, and sign up to take part at:

[bit.ly/Recruitment ESP2](https://bit.ly/Recruitment_ESP2)

For more information, please contact the ESP2 study team via [contact].

[**End of recruitment/update text**]

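### The eligibility rules let ESP2's own investigators, who developed the prediction form, enter predictions into its test and supply the targets and counts that score them; the likely effect is small and the remedy cheap.

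*Protocol*

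**What the plan says.** **Who may predict.** Under Study design, Inclusion criteria, the Protocol states: "The people providing predictions must be trial managers responsible for setting up trial recruitment sites and carrying out site initiation training with site staff". People with other job titles qualify if they do the same work. The single exclusion criterion is "Cluster randomised trials", which concerns the type of trial and not the person predicting. On volume: "There is no limit to the number of predictions a trial manager can make".

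**Where predictors come from.** The Recruitment section includes "within the Aberdeen Trials Unit, by word of mouth at meetings with staff at other Trials Units". Aberdeen also appears there as one of the five Trial Forge Centres.

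**Who built the form.** The Background says of the eight flags found in the pilot: "We used these red flags to develop a guided prediction form". The flyer in Appendix 1 says: "The project is led by trial managers based at the University of Aberdeen, UK".

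**Who supplies the score.** Under Follow-up, actual recruitment is compared with the target the manager gave when predicting. The same manager is asked for the site's recruitment total at 6 and 12 months, with an option to report a closed site or a changed timeline. Under Data collection, managers choose which sites to predict for.

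The Protocol has no provision to identify, exclude or separately analyse predictions made by ESP2 investigators.

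**The concern.** The Background presents ESP2 as the larger test of the form among trial managers across the UK and the world, and Research methods looks ahead to roll-out, including to less experienced managers. The figure of interest is therefore specificity in the hands of ordinary users. Someone who helped to design the form knows it better than those users will and has a stake in its success.

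That stake matters more here than in many prediction studies, because one person provides the target, the prediction and the outcome count and also selects the sites. The Protocol describes no independent check of the counts. If investigators predict better than other managers, or select or score sites more favourably even without intending to, pooled specificity will overstate what other users can expect. Registration is described as collecting brief demographic details, with no mention of study role, and none of the three planned subgroup analyses separates investigators from other managers.

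**Working it through.** The Protocol gives no figure for an investigator share, so there is none to reproduce. The check has two parts: whether the text admits investigators, and how much it could matter.

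**1. Does the text admit them?**
- The eligibility criterion is an activity: site set-up and initiation training.
- The project's leaders are described as trial managers, so those who do this work meet it.
- The exclusion criterion does not remove them.
- Their own institution is a named source.

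They are eligible. No sentence says they will register.

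**2. Share of predictions**

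Input (Sample size section): "In our pilot we got 56 predictions from one trials unit, ten trial managers and eight trials".
- Yield per manager: 56 / 10 = 5.6.
- Assumed insider group: ten people, the pilot's number. The Protocol does not say how many investigators set up sites.
- Share of the 1000 target: 56 / 1000 = 5.6%.
- Share of the 500 fallback: 56 / 500 = 11.2%.

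Specificity is estimated among failing sites only. If insiders' sites fail at the same rate as others (40% in the Sample size section), the shares carry over: 56 × 0.40 = 22.4 failing sites, out of 400 or 200.

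**3. Shift in pooled specificity**

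With share f, pooled specificity = f × Sp(insiders) + (1 − f) × Sp(others). The shift from the value among others is f × gap. The gap is assumed, since the documents give none; a range of 10 to 25 points is shown.

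| Predictions | f | Gap 10 points | Gap 25 points |
|---|---|---|---|
| 1000 | 5.6% | 0.56 | 1.40 |
| 500 | 11.2% | 1.12 | 2.80 |

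**4. Yardsticks**
- The Sample size section sets 75% against 70% for 1000 predictions, a distance of 5 points. The largest shift is 1.40 / 5 = 28% of it.
- For 500 predictions it sets 73% against 65%, a distance of 8 points. The largest shift is 2.80 / 8 = 35% of it.
- The 95% half-width at 75% with 400 failing sites is 1.96 × √(0.75 × 0.25 / 400) = 4.2 points; with 200 it is 6.0 points.

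The shift stays below sampling error in every cell. Unlike sampling error, though, it would not average out as predictions accumulate if the investigators' share stayed the same.

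**The case against.** The strongest case against is that this is a possibility and not an error. No sentence is wrong, no investigator is said to take part, and defining an analysis set is commonly left to an SAP. Each manager has a unique identifier and the team knows its own members, so investigators could probably be separated later. Much of this stands, and it limits the weight of the point. But eligibility and recruitment sources are fixed in the Protocol, and the separation is more credible if it is set before results are known.

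A reader might also infer more than the documents support:

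- *Insiders could supply an unlimited share.* No cap is set, but people may predict only for sites they set up, and should not predict twice for the same site in the same trial. For ten people, a 20% share of 1000 means 200 predictions, or 20 each, against 5.6 each in the pilot. The Protocol gives no basis for such a share.
- *A 20% share would lift 70% to the 75% target.* This needs that share and a 25-point gap (95% against 70%: 0.20 × 95 + 0.80 × 70 = 75). Neither comes from the documents. The only specificity reported for pilot managers is 32%, without the red flags.
- *Pilot managers developed the form.* They predicted without the red flags, and the study team is said to have built the form. The Protocol does not name the pilot's single trials unit.
- *The validation is not independent of development.* Predictions are prospective and scored against a target given beforehand. No model or cut-off fitted to pilot data is described, so no development data re-enter the test.
- *Insiders could raise specificity unnoticed by predicting failure freely.* The Analysis section also commits to sensitivity and both predictive values, so such a shift would tend to show as lower sensitivity. The incentive comes from the choice of primary outcome and is open to any participant.

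Self-reported targets and counts are likewise common to all participants. What is particular to investigators is that they combine this with a stake in the form.

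**Conclusion.** The point holds in a limited form. The eligibility criteria and recruitment sources allow ESP2's investigators, who developed the form, to contribute to its primary test and to supply the data that score their contributions. The documents do not show that this will happen or that the result would be seriously distorted.

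The estimated size, about 0.6 to 1.4 points of specificity at 1000 predictions and 1.1 to 2.8 points at 500, rests on three assumptions: ten insiders at the pilot's yield, the same failure rate at their sites as elsewhere, and a gap of 10 to 25 points in their favour. A higher yield per person would enlarge the shift; fewer participating investigators or a smaller gap would shrink it. The case for change is that the remedy is simple and makes the estimate refer to the form's intended users. Compulsory exclusion of all pilot managers from the primary estimate is debatable and does not follow from the text.

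**What to change.** 1. At registration, record whether the person is an ESP2 investigator and whether they made predictions in the pilot.
2. State in the Protocol that investigators' own predictions are excluded from the primary specificity estimate and reported separately.
3. Add a sensitivity analysis of specificity that also leaves out pilot participants.

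**Cost.** Two registration questions and a short addition to the eligibility or analysis text. At the pilot's yield, ten investigators would remove 56 predictions, or about 22 failing sites; fewer investigators would remove fewer. The 95% half-width at 75% would go from 4.2 to 4.4 points with 1000 predictions (1.96 × √(0.1875 / 377.6)), and from 6.0 to 6.4 points with 500 (1.96 × √(0.1875 / 177.6)). Even this loss can be avoided if the target of 1000 counts only predictions from people who are not investigators; the Sample size section describes the available pool as well over 1200 UK trial managers.
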